8.0	1.1	Shell Table 3	Added LV GLS (%). Erroneously this was not added to the table. LV GLS (%) was mentioned as an exploratory outcome in SAP version no. 1.0	November 3 rd 2023
8.0	1.1	Shell Appendix 2	Added "per day" in the Total physical activity, counts/min per day. Replaced "Walking" with stepping. Stepping was written by mistake.	November 3 rd 2023
8.0	1.1	Shell Appendix 4	Changed from mg to n(%). Our baseline data regarding concomitant medication do not support a sensible calculation of mean use in mg. Added "Other hypertensive" to include details on all hypertensive medication other than beta blocker. Added relevant comorbidities to differentiate the general health at baseline on the participant.	November 3 rd 2023

Abbreviations

bDMARD: Biological disease modifying anti rheumatic drug

BMI: Body mass index

BSA: Body surface area

CFAS: Centre for physical activity research, Rigshospitalet, Denmark

CI: Confidence interval

CMR: Cardiac magnetic resonance imaging

CONSORT: Consolidated Standards of Reporting Trials

csDMARD: Conventional synthetic disease modifying antirheumatic drugs

CVD: Cardiovascular disease

DAS28-ESR: Disease Activity Score-28 for rheumatoid arthritis with erythrocyte sedimentation rate

GLP: Glucagon-like peptide

HAQ-DI: health assessment questionnaire disability index

HIIT: High intensity interval training

IL-6: Interleukin-6

IL-6i: Interleukin-6 inhibitor

IQR: Interquartile range

ITT: Intention-to-treat

LVM: Left ventricular mass

MAR: Missing at random

NSAID: Non-steroid anti-inflammatory drug

PI: Principal Investigator

PP: Per protocol

RA: Rheumatoid arthritis

SAP: Statistical analysis plan

SD: Standard deviation

SE: Standard error

TNF: Tumour necrosis factor

TNFi: Tumour necrosis factor inhibitor

Table of contents

1 INTRODUCTION	5
1.1 BACKGROUND	5
1.2 DEVIATIONS FROM THE ORIGINAL PROTOCOL	5
1.3 AIM AND OBJECTIVES	5
1.4 HYPOTHESIS.....	6
2 METHODS	7
2.1 TRIAL DESIGN.....	7
2.2 RANDOMISATION	7
2.3 SAMPLE SIZE	7
2.4 FRAMEWORK.....	8
2.5 STATISTICAL INTERIM ANALYSES AND STOPPING GUIDANCE	8
2.6 TIMING OF ANALYSIS	8
2.7 TIMING OF OUTCOME ASSESSMENTS.....	8
3 STATISTICAL PRINCIPLES.....	9
3.1 CONFIDENCE AND P-INTERVALS	9
3.2 ADHERENCE AND PROTOCOL DEVIATIONS	9
3.3 ANALYSIS POPULATION	10
4 TRIAL POPULATION.....	10
4.1 SCREENING DATA.....	10
4.2 ELIGIBILITY CRITERIA.....	10
4.3 RECRUITMENT	10
4.4 BASELINE CHARACTERISTICS	10
5 ANALYSIS.....	11
5.1 OUTCOMES AND DEFINITIONS	11
5.2 ANALYSIS METHODS.....	12

1.1 Background

Rheumatoid Arthritis (RA) is a chronic autoimmune disease with joint inflammation and destruction, and increasing cardiovascular disease (CVD) risk compared to the background population (1–4). Dysregulated immune response leads to elevated pro-inflammatory proteins like tumour necrosis factor (TNF) and interleukin-6 (IL-6), contributing to systemic inflammation (5,6). Exercise is a corner-stone treatment for RA and has immunomodulatory effects where IL-6 plays a central role (7). Exercise-induced IL-6 has positive effects on fat loss and cardiac function (8,9). High intensity intermittent training (HIIT) is recommended for improving cardiovascular fitness (10). Studies on the impact of IL-6 inhibitors (IL-6i) during exercise in RA patients are lacking, making it valuable to explore in clinical trials. Comparing RA patients treated with IL-6i and TNF inhibitors (TNFi) during exercise training could offer novel insights into the effects of biological disease modifying anti rheumatic drugs (bDMARDs) in relation to exercise.

1.2 Deviations from the original protocol

The present statistical analysis plan (SAP) incorporates outcomes of particular interest to exercise-induced cardiac adaptions. Several secondary outcomes denoted in the original protocol and at clinicaltrials.gov were erroneously labeled and indicated as key secondary outcomes and will not feature in the present SAP (Shell Appendix 1). In the original protocol, the trial end criteria were mistakenly denoted in the following way “(...) control and further inclusion rate is below two patients per month.” This has been changed to “(...) control or further inclusion rate is below two patients per month” in the SAP (see Statistical interim analyses and stopping guidance).

1.3 Aim and objectives

Primary aim:

To investigate if the effects of exercise training on cardiac structure and function in RA patients vary depending on the concomitant treatment with either TNFi or IL-6i.

Primary objective:

To evaluate whether concomitant use of one of the two different bDMARDs impact the effect of 12 weeks of regular supervised exercise, relative to treatment as usual, on changes in left ventricular mass (LVM, measured in grams [g]) measured by cardiac magnetic resonance imaging (CMR) from baseline to week 12, in RA patients in stable treatment with either a TNF- or IL6-inhibitor.

Key secondary objectives:

To explore, in patients with RA in stable treatment with either a TNF- or IL-6-inhibitor, whether concomitant use of one of the two different biologics impact the effect of 12 weeks of regular supervised exercise, relative to treatment as usual, after 12 weeks on changes in:

1. Left ventricular stroke volume
2. Left ventricular end diastolic volume
3. Relative VO₂peak
4. Disease Activity Score-28 for rheumatoid arthritis based on the erythrocyte sedimentation rate

Other secondary objectives:

Further to explore the effect of concomitant use of one of the two different biologics impact the effect of 12 weeks of regular supervised exercise, relative to treatment as usual, after 12 weeks on changes in:

- LVM/body surface area
- Left ventricular global longitudinal strain
- Left ventricular ejection fraction
- Left ventricular end-systolic volume
- Absolute VO₂peak
- Total lean mass
- Total fat mass
- Resting heart rate

1.4 Hypothesis

We hypothesise that pharmacological inhibition of IL-6 (unlike TNFi) impairs exercise-induced changes in LVM. The null hypotheses are that there is no difference between the exercise and control group, and this apparent null effect cannot be effect modified by the concomitant choice of biological agent (IL-6i vs TNFi).

2 Methods

2.1 Trial design

All procedures and detailed information about the design, assessments, inclusion and exclusion criteria and interventions has been published elsewhere (11). Briefly, this study is a single-centre, randomised, parallel group, investigator-blinded trial with a primary endpoint of changes in LVM after 12 weeks measured by cMRI. The study was designed to include 80 participants: After patients signed the informed consent form, participants were randomised to either exercise (experimental intervention) or no exercise (control comparator).

2.2 Randomisation

The randomisation was based on a 1:1 stratified block randomisation (with blocks of 10). Participants were stratified for bDMARD treatment (TNFi vs IL-6i) and sex (male vs female) as part of the randomisation. The randomisation list was kept in a secure file, accessible only by an employee at Centre for Physical Activity Research (CFAS) not affiliated with this study.

2.3 Sample size

The sample size and power considerations is also described in the published protocol (11). For the primary outcome change in left ventricular mass assessed after 12 weeks measured by MRI scan, to detect a change of 12 g (SD 12.3) between exercise groups (TNFi vs IL-6i) assuming a 5% alpha-level in a two-sided unpaired t-test with homoscedasticity and a power of 80% ($1-\beta$), a sample size of 16 in each group is needed. To account for potential dropouts, we decided to include 20 patients in each stratum*group ($n=80$). No previous studies have determined the effect of TNF on cardiac adaptations following exercise, thereby limiting our power analysis to either placebo or IL-6i.

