2.4 Framework

The study was designed as a superiority trial, testing the effect of exercise compared to control, and explore the possible ‘effect modifying impact’ of IL6i (11) as a contextual factor. Statistical analyses of RCTs respecting the intention-to-treat population yield a causally valid estimate of the average treatment effect, which is the contrast between the outcomes in the two randomised treatment groups commonly accompanied by a confidence interval. The primary objective of the RABEX Trial however is to examine whether any observed treatment effect varies across patient subgroups; i.e., whether the treatment effect is modified by the value of a variable assessed at baseline (12).

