5.2 Analysis methods

The main analysis (primary outcome) will compare TNFi and IL-6i in terms of change of LVM from baseline to follow-up after an exercise intervention of 12 weeks (Shell Table 2 and Shell Figure 2). We will assess this superiority analysis based on the ITT population. Change from baseline will be calculated as the value collected after 12 weeks minus the initial value; An increase in LVM indicates cardiac adaptions to exercise. To analyse the change from baseline, we will use an ANCOVA model, and report the least squares means with standard errors. For the main analyses, missing values will be replaced by a simplistic non-responder imputation technique (i.e., baseline observation carried forward). The model will include the level at baseline as a covariate, and fixed effect factors for sex, group (Exercise vs Management as usual), and concomitant bDMARD use (TNFi vs. IL-6i). For the purpose of sensitivity analysis, we will also attempt to account for baseline values and previous bDMARDs treatment (number of drugs used prior to the treatment at enrollment).

$$\Delta LVM = \text{Group} + \text{sex} + \text{bDMARD} + \text{Group} * \text{bDMARD} + f(LVM_{\text{baseline}})$$

The primary analysis will be conducted following week 12 based on the change from baseline variable (e.g., ΔLVM). We will report the difference between the randomised groups with a 95% CI and the associated P-value, which tests the null hypothesis of no difference between the groups.

We will claim superiority if the calculated 95% CI of the estimated group difference in the change from baseline does not include 0 in the ITT population. To ensure the validity of our model, several assumptions will be assessed. These include checking for normal distribution of the residuals and assessing the homogeneity of the variance by examining the standardized residuals in relation to the predicted values. In cases where variables do not meet the model assumptions, appropriate transformations will be applied to address the issue. However, if no suitable transformation is found, the results will be reported in terms of median change along with interquartile ranges. In such instances, suitable non-parametric statistical tests will be employed for analysis and testing.

Analysis of secondary outcomes will follow the same method as described above. Results will be presented in Shell table 2.

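### SAP 2.3: for the t-test it names, 16 per group gives about 76% power, not 80%; 80% needs 18 per group

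*SAP*

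**What the plan says.** Section 2.3 (Sample size) gives the whole calculation for the primary outcome. The target is "to detect a change of 12 g (SD 12.3) between exercise groups (TNFi vs IL-6i"). The test and error rates are fixed by "assuming a 5% alpha-level in a two-sided unpaired t-test with homoscedasticity" and by a stated power of 80%. The result is "a sample size of 16 in each group is needed".

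The section then moves from 16 to 20: "To account for potential dropouts, we decided to include 20 patients in each stratum*group", 80 patients in all. It states no dropout rate. It mentions that the published protocol also describes the calculation, but it restates every input itself.

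**The concern.** The test, sidedness, variance assumption, alpha, difference, SD, power and equal group sizes all stand in one sentence, so the required number can be recomputed without outside information. It comes out at 18, not 16. Put the other way, 16 per group carries a type II error of 23.9% where the SAP states 20%.

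This is the SAP's only power statement and it concerns the primary outcome. Anyone who repeats the calculation will find the mismatch. What is at stake is whether the reported design figure can be reproduced. The validity of the analysis is not affected.

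**Working it through.** **Inputs, all from SAP 2.3.** Difference 12 g; SD 12.3 g; two-sided alpha 0.05; unpaired equal-variance t-test; power 80%; equal groups; stated result 16 per group.

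**Exact power for the named test.** The standardised difference is d = 12/12.3 = 0.9756. With n per group the test has 2n − 2 degrees of freedom and noncentrality d × √(n/2). Power is the probability that the noncentral t exceeds the two-sided 5% critical value in either direction.

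| n per group | df | critical t | noncentrality | power |
|---|---|---|---|---|
| 16 | 30 | 2.042 | 2.759 | 76.1% |
| 17 | 32 | 2.037 | 2.844 | 78.8% |
| 18 | 34 | 2.032 | 2.927 | 81.1% |
| 20 | 38 | 2.024 | 3.085 | 85.2% |

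The unrounded n for 80% power is 17.51, so 18 per group. A simulation of 400,000 trials at n = 16 gave 76.2%, in agreement.

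**Attempts to recover 16.**

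- Normal approximation: n = 2 × (1.95996 + 0.84162)² × (12.3/12)² = 2 × 7.849 × 1.0506 = 16.49. A required n rounds up, to 17. Even under this formula 16 gives 78.8% power and 17 gives 81.2%.
- Normal approximation with the small-sample term: 16.49 + 1.95996²/4 = 17.45, so 18.
- One-sided t-test: 13.72, so 14. The SAP says two-sided in any case.
- Rounded inputs: with both at their favourable edge, 12.49 g and SD 12.25, power at 16 is 79.7%.
- Break-even: 16 per group reaches 80% only with a difference of about 12.59 g or an SD of about 11.72 g. Neither would print as 12 or 12.3.

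No variant gives 16 when rounded up. The stated 16 equals 16.49 rounded down. That is a possible origin, but the SAP does not say so.

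**Why 85% at 20 per cell needs a caveat.** Section 2.4 says that the primary objective "is to examine whether any observed treatment effect varies across patient subgroups", and the model in 5.2 carries a group-by-bDMARD term. An interaction contrast draws its variance from four cells instead of two. The following assumptions are not in the SAP: an interaction difference also equal to 12 g, SD 12.3 in all four cells, 20 per cell, and 80 − 6 = 74 residual degrees of freedom.

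- Covariates explain none of the variance of change: SE = 12.3 × √(4/20) = 5.50, noncentrality 12/5.50 = 2.18, power 57.7%.
- Covariates explain 25%: SE = 5.50 × √0.75 = 4.76, noncentrality 2.52, power 70.1%.

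These two figures show only that 85% must not be read as the power of the interaction test. They play no part in showing the error in 2.3.

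**The case against.** The strongest case against accepts the arithmetic and disputes its importance.

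- **The trial planned 20 per cell, not 16.** At 20 the named contrast has 85.2% power, and at 18 evaluable it still has 81.1%. This stands, and it is why the consequence is minor. It does not make the sentence right, because the SAP presents 20 as a dropout allowance on top of a required 16.
- **The planned analysis is an ANCOVA.** Adjustment for baseline and sex could lower the residual SD, and the break-even SD needs covariates that explain only 1 − (11.72/12.3)² = 9% of the variance. That is fair, so 76% must be read as the power of the planning t-test. But 2.3 claims no such gain and names an unadjusted test.
- **The change comes late.** Section 2.5 describes inclusion as ended, and the published protocol, which is not at hand, may carry the same figure. This limits the benefit. It does not excuse a figure that the SAP states in full.
- **Writing 76% in place of 80% alters the record of the design target.** This has some force. It is met by wording that keeps 80% visible as the target and gives 76% as what 16 per group delivers.
- **The interaction figures rest on outside assumptions.** True. They serve only as the reason for a caveat, and drop out if the 85% figure is not quoted.

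**Conclusion.** The stated sample size does not give the stated power for the stated test. Sixteen per group gives 76.1%, 3.9 points below 80%; 80% needs 18 per group, 2 more than stated (36 in the two exercise groups against 32). The result rests only on the inputs printed in 2.3 and on exact calculation for the test named there.

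The size of the problem is modest. No claim is made about the adequacy of the dropout margin: 2.3 gives no dropout rate, and under 5.2 "missing values will be replaced by a simplistic non-responder imputation technique (i.e., baseline observation carried forward"), so dropouts stay in the main analysis. Nor is any claim made about the use of 16 in the rule for ending inclusion in 2.5. The sentence should be corrected because it is the design statement for the primary outcome and cannot be reproduced as written.

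**What to change.** Amend one sentence in 2.3, in one of two ways:

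- keep 16 per group, and say that it was planned for 80% power but gives about 76% under the named t-test; or
- say that the named t-test needs 18 per group for 80% power.

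The first keeps visible the number that the design used. If the planned 20 per cell is mentioned, add that it gives about 85% power for the two-group TNFi versus IL-6i exercise contrast when all are evaluable, and that this figure does not apply to the group-by-bDMARD interaction test in 5.2. A dated entry in the SAP's change log would explain any difference from the published protocol.

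The cost is one sentence of wording and a slightly less favourable figure. Enrolment, the analysis and section 2.5 stay as they are.

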2.4 Framework

The study was designed as a superiority trial, testing the effect of exercise compared to control, and explore the possible ‘effect modifying impact’ of IL6i (11) as a contextual factor. Statistical analyses of RCTs respecting the intention-to-treat population yield a causally valid estimate of the average treatment effect, which is the contrast between the outcomes in the two randomised treatment groups commonly accompanied by a confidence interval. The primary objective of the RABEX Trial however is to examine whether any observed treatment effect varies across patient subgroups; i.e., whether the treatment effect is modified by the value of a variable assessed at baseline (12).

2.5 Statistical interim analyses and stopping guidance

No interim analyses were planned. Inclusion period ended 26 months after the first subject had been recruited or if at least 16 subjects in each group have been deemed fully compliant to intervention or control or further inclusion rate was below two patients per month.

2.6 Timing of analysis

The analysis described in this SAP will take place once all trial participant has completed either the follow-up cMRI, the follow-up cMRI and the follow-up visit at CFAS or deemed lost to follow-up by the project coordinator or Principal Investigator (PI). The data for the primary outcome is expected to be received by mid October 2023.

2.7 Timing of outcome assessments

Following informed consent, patients underwent baseline assessments at CFAS and the Department of Cardiology, Rigshospitalet. Patients were randomised no later than one day after baseline completion (study day 3, week 0). At week 6 (day 38-45) study participants complete a self-reported three-day kcal intake. The week 12 follow-up visits took place at day 88 – 112 after randomisation. At the follow-up at CFAS, a 5-day activity monitor will be placed on the patient (Shell Appendix 2).

3 Statistical principles

3.1 Confidence and p-intervals

All P values and 95% confidence intervals will be two sided with an alpha-level of 0.05. In principle, $P < 0.05$ will be considered statistically significant *per se*; instead of applying explicit adjustments for multiplicity, we will examine and interpret all secondary objectives in a prioritized order using a "gatekeeping procedure" (see 5.1 Outcome definitions) (13). This means we will sequentially assess and interpret the secondary outcomes until either a statistically significant difference is not found, or all analyses have been completed at a statistical significance level of 0.05 following the outcome measure hierarchy listed in this SAP.

3.2 Adherence and protocol deviations

Adherence to the study is defined by compliance to the family of bDMARD each participant received prior to enrollment in this study of no less than 80%. Furthermore, adherence to the intervention (exercise) is defined by attendance of no less than 80% of the scheduled sessions (Shell appendix 3).

Adherence to the bDMARD treatment will be calculated as the amount (in mg) of bDMARDs that were taken during the study period divided by the supposed amount to have been taken during the study period:

$$\text{Adherence (\%)} = \frac{\text{Amount (mg) of bDMARD taken during study period}}{\text{Amount (mg) of bDMARD supposed to have been taken during study period}} * 100$$

Adherence to the intervention (exercise) will be calculated as the number of exercise sessions attended divided by the total number of exercise sessions intended in the study (36 sessions)

$$\text{Adherence (\%)} = \frac{\text{Exercise sessions attended}}{36} * 100$$

Adherence will be reported as number of participants with adherence no less than 80%. The intention-to-treat (ITT) population will serve as denominator. If protocol deviations are believed to impact the accurate evaluation of the trial, they are categorized as significant and will be managed as violations of the protocol.

The following are considered protocol violations:

1. Non-adherence to bDMARD treatment
2. Non-adherence to the exercise intervention

PI ([name]) and project coordinator (SJ) will review each case and determine if that participant should be excluded from per-protocol (PP) analysis, prior to unblinding. Data regarding protocol deviations will be summarized by group with details for specific deviation(s) given.

3.3 Analysis population

The main analyses will be performed on the ITT population. Among patients with baseline data available, the ITT principle asserts the effect of a treatment policy (that is, the planned treatment regimen), rather than the actual treatment given (i.e., it is independent of treatment adherence). Accordingly, participants with a baseline visit at CFAS and a LVM (g) measured by CMR at baseline were subsequently allocated to a treatment group (Exercise and Control, respectively) and were followed up, assessed, and analysed as members of that group, irrespective of their adherence to the planned course of treatment (i.e., independent of withdrawals and cross-over phenomena). In contrast, The PP population is defined as participants who had their baseline measures available and completed the trial without protocol violations and a completed CMR at follow-up.

4 Trial Population

4.1 Screening data

A complete list of screening data, as well as eligibility (reasons provided), inclusion, exclusion, withdrawals and lost to follow-up (reasons provided) will follow the CONSORT standard flow diagram (Shell Figure 1) (14).

4.2 Eligibility criteria

Inclusion and exclusion criteria have previously been published (11).

4.3 Recruitment

The recruitment process have previously been published (11).

4.4 Baseline characteristics

The demographics and baseline data for the ITT population will be depicted in a table (Shell Table 1 and Shell Appendix 4). The data will be depicted as means and SD (normal distribution) or median and IQR (non-normal distribution). Categorical data will be depicted as numbers and percentages.

5 Analysis

5.1 Outcomes and definitions

The total list of outcomes is published elsewhere (11).

Outcomes for the current (primary) manuscript are prioritized in the following ranking:

1. Change from baseline in LVM
2. Change from baseline in left ventricular stroke volume
3. Change from baseline in left ventricular end diastolic volume
4. Change from baseline in relative VO_{2peak}
5. Change from baseline in DAS28-ESR

Outcome definitions

1. LVM refers to the mass or weight (g) of the muscular wall of the left ventricle. Measured by CMR.
2. Left ventricular stroke volume is the amount of blood ejected from the left ventricle of the heart during one contraction (systole) and into the aorta. Measured by CMR.
3. Left ventricular end diastolic volume is the amount of blood present in the left ventricle at the end of the diastolic phase. Measured by CMR.
4. Relative VO_{2peak}, or maximal oxygen consumption per kg (ml/min/kg), is a measure of the maximum amount of oxygen an individual can use during intense aerobic exercise. Measured by indirect calorimetric measurements at CFAS (11).
5. DAS28-ESR is a composite numerical score used to assess the disease activity and monitor the progress of RA patients. The DAS28-ESR score takes into account 28 tender and swollen joint

counts, the ESR and the patient's assessment of their overall well-being on a visual analogue scale.

